1.3. Study Design

This is a multi-center, single-arm, Phase 2 open label treatment study to determine the efficacy, safety, tolerability, and pharmacokinetics of nirogacestat in adult participants with recurrent OvGCT. Participants must have received at least one prior course of systemic therapy for OvGCT and have measurable disease by RECIST v1.1 to meet the eligibility criteria.

The Schedule of Assessments (SoA) is in protocol Section 1.3, Table 2. Participants will be screened up to 28 days prior to the first dose of study treatment (nirogacestat) and full eligibility will be based on the inclusion and exclusion criteria (Protocol Section 7.1 and 7.2).

Participants will administer 150 mg (3 × 50 mg tablets) of study treatment BID, continuously in 28-day cycles. Participants will remain on study treatment until death, disease progression (unless the participants meet criteria for continued treatment), discontinuation of study treatment for any reason, the study is stopped by the Sponsor for any reason, or participant qualifies for Sponsor's Compassionate Use Program.

All scans will be performed and read locally by the site's radiologist for Tumor assessment as per RECIST v1.1. Same modality used at Screening must be used at each subsequent imaging visits. Baseline scan is defined as scans performed prior to first dose of study treatment. On treatment scans are performed every 8 weeks (C3D1, C5D1, C7D1) for the first 6 months and then every 12 weeks (C10D1, C13D1, etc.) thereafter. Scans may be performed (-) 7 days prior to the visit.

The final 2-year survival check-in will occur approximately 2 years after the first dose of study treatment. If participant discontinues from study treatment prior to the 2-year check-in, quarterly telephone or email contact following EOT is required until the 2-year survival data point has

been collected. In addition, collection of subsequent anticancer therapy after nirogacestat and overall response to this therapy will be recorded. Only information about the subsequent therapy used directly after nirogacestat is required along with the final survival outcome at the 2-year check point.

Participants who discontinue study treatment early for any reason should return to the clinic for an End of Treatment (EOT) visit within 7 days after the Investigator determines study treatment will no longer be used and then again for a safety Follow-up (FUP) visit 30 days (+7 days) after the last dose of study treatment.

The estimated study duration is 3 years, and all participants will be followed for at least 2 years (unless the study is prematurely stopped due to futility).

A Bayesian strategy allowing continuous monitoring will be used to evaluate the posterior distribution of ORR (complete + partial) ([Lee and Liu 2008](#); [Chen et al. 2019](#)) and the study may be stopped for futility if necessary. There will be no pause in accrual for interim assessments.

1.4. Sample Size Determination

A prior GOG phase 2 trial in previously treated participants with stromal tumors evaluated the efficacy and safety of bevacizumab monotherapy in participants with recurrent sex cord stromal tumors of the ovary. The ORR in this study was 16.7% ([Brown et al. 2014](#)). Following this outcome, the ALIENOR/ENGOT ov7 trial randomized participants to see if the addition of bevacizumab to paclitaxel had effect on the PFS rate among participants with relapsed ovarian sex cord stromal tumors. While the combination therapy of paclitaxel and bevacizumab showed an ORR of 44% over paclitaxel monotherapy, the PFS remained equivocal between the two treatment groups ([Ray-Coquard et al. 2020](#)). Based on the ORR from the bevacizumab monotherapy trial, this study aims for an ORR of 30% with PFS as a secondary endpoint.

Since this is a first-in-human proof of concept study for the indication, no formal hypothesis testing or sample size calculation is contemplated. The initial goal of accrual for this study is 43 participants which should provide sufficient sample size for interim evaluations for futility with a Bayesian strategy of continuous monitoring. Participant accrual will not be paused during the interim evaluations. The Bayesian approach to be used for futility analysis assumes a

beta-binomial distribution with an uninformative prior of beta distribution ([Lee and Liu 2008](#); [Chen et al. 2019](#)). Assume at an assessment point, the study has accrued X responders out of n (≤ 43) participants. With a prior distribution of *beta* (a, b), X follows a binomial distribution and the posterior distribution of the response rate follows a beta distribution with parameters $(a+x, b+n-x)$, where x is the observed value of X . Thus, the number of responses in the potential $(43-n)$ future participants, Y , follows a beta-binomial distribution with parameters $(43-n, a+x, b+n-x)$. From the observed responders x and a target ORR, the predictive probability of reaching the target ORR at the end of study can be calculated with the beta-binomial distribution. If the predictive probability is too low, e.g., $\leq 10\%$, the study may be terminated for futility. A high predictive probability, e.g., $>85\%$, suggests high likelihood of achieving treatment efficacy at the end of the study.

For this study, we assume that a response rate of $\leq 15\%$ at the end of study is considered ineffective for the treatment, and enrollment will stop if the posterior probability of ORR $>15\%$ is less than 0.1. On the other hand, the treatment is considered promising if the posterior probability of ORR $>15\%$ is higher than 0.85, that is, if the posterior distribution provides

$$Prob\{ORR > 0.15 | data\} > 0.85.$$

For calculating the posterior probability, a prior of beta $(0.1, 0.9)$ could be assumed. These parameters $(0.1$ and $0.9)$ of the beta prior correspond to the initial assumed distribution of ORR with mean equal to $0.1/(0.1+0.9) = 10\%$ (that is, an initial belief of ORR around 10%). The beta parameters will be updated according to observed number of responders at each analysis.

Given the cutoff points of the predictive probability for futility and efficacy, the characteristics of the design can be assessed in terms of type I and II errors. For example, if the cutoff points are set at 10% for futility and 85% for efficacy, the above Bayesian rule will result in futility stopping boundaries of 1, 2, and 5 or fewer respondents if interim evaluations were to occur at enrollment of 10, 20, 30 participants, respectively. If the true rate of ORR is 15%, the chance to conclude treatment efficacy at the end of the study is 7% (Type I error). However, the probability to stop the trial early is 79%. If the true rate of ORR is 30%, the chance to conclude treatment efficacy at the end of the study is 76%.

A set of simulations using a frequentist framework under the similar interim evaluation schedule as above are performed for comparisons. Specifically, the type I and II errors are simulated for scenarios where the study ceases for futility when the ORRs are 0%, $\leq 5\%$, $\leq 10\%$, or 15% when 10, 20, 30, and 43 participants have been enrolled, respectively. Those conditions correspond to stopping for futility when there are fewer than or equal to 0, 1, 3, and 6 respondents in the three interim and final analyses, respectively. Table 1 below provides results based on 10,000 simulations of probability of early stopping for futility and the expected overall sample sizes.

Table 1 Simulated Probability of Early Stopping under Assumed ORR

Interim Time Point (Enrollment at N =)		10	20	30	43	Futility at First Three Looks	Futility at End of Study	Efficacy at End of Study	Average Overall Sample Size ¹
Stopping Boundary (No. of Responders)		0	1	3	6				
Assumed True Underlying ORR	0.05	0.60	0.19	0.16	0.05	0.95	1.00	0.00	11
	0.10	0.35	0.13	0.21	0.19	0.69	0.88	0.12	22
	0.15	0.20	0.07	0.13	0.19	0.40	0.59	0.41	32
	0.20	0.11	0.03	0.06	0.10	0.20	0.30	0.70	38
	0.25	0.06	0.01	0.02	0.03	0.09	0.12	0.88	41
	0.30	0.03	0.00	0.01	0.01	0.04	0.04	0.96	42

ORR = Objective Response Rate, N = Sample size; No. = Number

¹Without considering newly enrolled participants while the interim evaluation is ongoing.

As can be seen from the above table, the probabilities to stop for futility early if true ORR is either 5% or 10% are approximately 100% and 88%, respectively. The probabilities to stop for futility when true ORR is either 25% or 30% are approximately 12% and 4%, respectively. For various criteria to claim efficacy, the exact 95% CI for different corresponding observed ORR based on the Clopper-Pearson method are listed in Table 2. For example, if the total sample size is 20 at the second interim evaluation, the lower bound of the 95% CI will be 27.2% if the observed ORR is 50%. When the total sample size is 30 or higher and the observed ORR is 50%, the lower bound of the 95% CI will be $\geq 31.3\%$.

Table 2 Exact 95% CI Given Observed ORR

Minimum ORR to Claim Efficacy	Sample Size	Observed No. of Responders	Observed ORR (%)	95% Confidence Interval	
				Lower Bound	Upper Bound
0.25	10	3	30.0	6.7	65.3
	20	5	25.0	8.7	49.1
	30	8	26.7	12.3	45.9
	43	11	25.6	13.5	41.2
0.3	10	3	30.0	6.7	65.3
	20	6	30.0	11.9	54.3
	30	9	30.0	14.7	49.4
	43	13	30.2	17.2	46.1
0.5	10	5	50.0	18.7	81.3
	20	10	50.0	27.2	72.8
	30	15	50.0	31.3	68.7
	43	22	51.2	35.5	66.7

CI = Confidence Interval; ORR = Objective Response Rate

1.5. Data Monitoring Committee

There is no Data Monitoring Committee for this study.

2. ANALYSIS SETS

2.1. Analysis Set Definitions

The following participant analysis sets will be evaluated and used for presentation and analysis of the data:

- Screened Analysis Set: The Screened Analysis Set will consist of all participants who signed the informed consent.
- Full Analysis Set: The Full Analysis Set will consist of all participants who received at least 1 dose of nirogacestat treatment.
- PK Analysis Set: The PK Analysis Set will consist of all treated participants with at least 1 non-missing value in serum concentration of nirogacestat.
- Safety Analysis Set: The Safety Analysis Set will consist of all participants who received at least 1 dose of nirogacestat treatment.

The Full Analysis Set is the same as the Safety Analysis Set. All efficacy analyses will be based on the Full Analysis Set. All safety analyses will be based on the Safety Analysis Set.

2.2. Protocol Deviations

Protocol deviations are reviewed in accordance with the Protocol Deviation Management Plan.

All Major and Minor protocol deviations will be reviewed by SpringWorks prior to database lock. The protocol deviation categories are defined in the Protocol Deviation Management Plan, including those related to the inclusion/exclusion criteria, informed consent, withdrawal criteria, study treatment, etc. Major protocol deviations and the COVID-19 related major protocol deviations will be summarized. A data listing of all PDs including a description of the deviation will be generated, and the COVID-19 related protocol deviations will be flagged.

2.3. Impacts from COVID-19

This study was conducted during the global SARS-Cov-2 pandemic. The impact of COVID-19 was mitigated based on the evolving EMA and FDA COVID-19 guidelines [[European Medicines Agency 2021](#); [US Food and Drug Administration 2020](#)].

A listing of all participants impacted by COVID-19 and how their participation in the study was altered, including missed visits, missed assessments, impacts on the tumor assessments, and other deviations from protocol procedures due to COVID-19 will be provided.

3. ENDPOINTS

3.1. Primary Efficacy Endpoint

The primary efficacy endpoint is objective response rate, defined as the proportion of participants with CR + PR using RECIST v1.1. See Section 8.1 for the details of RECIST Criteria v1.1.

Study participants who have no post-baseline tumor assessment and those whose best overall response is not evaluable or less than CR or PR will be analyzed as a non-responder.

3.2. Secondary Efficacy Endpoints

Secondary efficacy endpoints include:

- PFS-6, defined as the survival probability of not having progressed or died at 6 months follow-up. Progression is defined by RECIST v1.1.
- Two-year overall survival at 2 years (OS-2), defined as the survival probability of being still alive at 2 years of follow-up after their first dose of nirogacestat.
- Change from baseline in FOSI.
- DoR, defined as the time from first assessment of response (CR + PR using RECIST v1.1) to first disease progression defined by RECIST v1.1 or death, whichever comes first.

3.3. Exploratory Efficacy Endpoints

Exploratory endpoints include:

- Progression free survival (PFS), defined as time from first dose of nirogacestat to first disease progression on nirogacestat or death from any cause, whichever comes first.
- Progression free survival on continued nirogacestat treatment, defined as time from first disease progression per RECIST v1.1 to second disease progression on continued nirogacestat treatment confirmed by investigator discretion or death, whichever comes first.
- Progression free survival 2 (PFS2), defined as time from first dose of nirogacestat to second disease progression on subsequent line of anticancer treatment (after nirogacestat)

confirmed by investigator discretion at long term safety follow-up visit or death, whichever comes first.

- Overall survival (OS), defined as time from first dose of nirogacestat to death from any cause.
- Time to response, defined as time in months from first dose until date of the first documented response (CR or PR).
- Evaluate Next Generation Sequencing (NGS) status in baseline tumor tissue.
- Change from baseline in:
 - Inhibin A&B, Follicle-stimulating, hormone (FSH), estradiol, CA-125, and Mullerian Inhibiting Substance (MIS) / AMH
 - Circulating tumor DNA (ctDNA) (if data are available)
- Baseline NICD expression in tumor tissue (if data are available).

3.4. Safety Endpoints

Key safety endpoints will include incidence of treatment-emergent Adverse Events (TEAEs), changes in clinical laboratory parameters, vital signs, physical examination findings, and electrocardiograms (ECGs).

Tolerability will be assessed according to toxicities graded by National Cancer Institute Common Terminology Criteria for Adverse Events (CTCAE) v5.0.

3.5. Pharmacokinetic Endpoints

Pharmacokinetic endpoints include C_{trough} and 1-hour post-dose serum concentrations of nirogacestat.

3.6. Other Endpoints

Not applicable.

4. STATISTICAL METHODOLOGY

4.1. General Information

All data listings that contain an evaluation date will have a relative study day associated with treatment start (Rel Day). Pre-treatment and on-treatment study days represented as Relative Day are numbered relative to the day of the first dose of study medication which is designated as Day 1. The preceding day is Day -1, the day before that is Day -2, etc.

Tabulations will be produced for appropriate disposition, demographic, baseline characteristics, efficacy, and safety parameters. For categorical variables, summary tabulations of the number and percentage of participants within each category (with a category for missing data) of the parameter will be presented. For continuous variables, the number of participants, mean, median, standard deviation, minimum, and maximum values will be presented. Time-to-event data will be summarized using 25th, 50th (median) and 75th percentiles and time point survival probabilities (at 6 months, 1 year, 18 months, 2 years, etc.) with associated 2-sided 95% confidence intervals (CIs) using Kaplan-Meier methodology and the log-log transformation, as well as number and percentage of events and censored observations.

Graphical displays will be provided where useful to aid in the interpretation of results. A swimmer plot may be used to present the exposure to study treatment, overall response and follow up for all participants in the Full Analysis Set. Each participant will be presented on a horizontal bar (y-axis) over time (x-axis) starting at treatment start date. For each participant's bar, the plot will include best overall response (CR, PR, SD, PD, or NE), end of response or continued response (at censored timepoint).

The following conversion conventions will be applied:

- CIs will be presented to 1 more decimal place than the raw data
- Weeks will be calculated as number of days divided by 7
- Months will be calculated as number of days divided by 30.4375
- Years will be calculated as number of days divided by 365.25
- Cycles as used in adverse event summaries are defined as every 28 days
- Day 1 will be considered as the first day of treatment

All tables, figures, and listings will include footers at the bottom of the page reflecting the path of the programs used to generate the tables, figures, and listings, and date and time of the generation of the output.

All descriptive statistical analyses will be performed using SAS statistical software Version 9.4 or higher. Medical history and adverse events will be coded using the Medical Dictionary for Regulatory Activities (MedDRA) Version 27.0. Concomitant medications will be coded using the World Health Organization (WHO) Drug Dictionary Version March 2022 or later.

4.2. Baseline Definitions

For all analyses, baseline will be defined as the last non-missing value prior to the first administration of study treatment.

4.3. Methods of Pooling Data

Data will be pooled across study sites.

4.4. Adjustments for Covariates

In this single arm study, covariate adjustment will not be used unless specified otherwise.

4.5. Multiple Comparisons/Multiplicity

Since this is a first-in-human proof of concept study for the indication, no formal hypothesis testing is contemplated. Hence there is no multiplicity adjustment for the primary or secondary efficacy endpoints.

4.6. Subgroups

Subgroup analyses for the primary endpoint ORR are not predefined due to the following reasons:

- This is a single arm study with a small sample size.
- The anticipated response rate is low-to-medium.

However, post-hoc analysis for subgroup analyses will be performed if deemed necessary.

4.7. Withdrawals, Dropouts, Loss to Follow-up

Participants who are withdrawn or discontinue from the study will not be replaced.

4.8. Missing Data Conventions for Efficacy Endpoints

There will be no imputation or substitutions made to accommodate missing efficacy data points. All data recorded on the eCRF will be included in data listings that will accompany the CSR.

4.9. Missing Data Conventions for Safety Endpoints

4.9.1. Handling of Missing/Partial Dates for AEs

Adverse events with incomplete onset dates will be handled as follows for the purpose of determining treatment emergence.

1. If the month and day are missing:

- If the year of the event is the **same** as the year of the first dosing date, then the day and month of the first dosing date will be assigned to the missing fields.
- If the year is **prior to** the year of first dosing date, then December 31 will be assigned to the missing fields.
- If the year is **after** the year of first dosing, then January 1 will be assigned to the missing fields.

2. If the day is missing:

- If the month and year are the same as the month of treatment, the onset date will be assigned to the date of treatment.
- If the month and year are not the same as the month/year of treatment, then the onset day will be set to the first day of the month.

If the start date is completely missing and end date is not before the first dose of study treatment, then the adverse event will be considered treatment emergent.

If the participant has died and the imputed date is later than the date of death, the date of death will be used.

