### 11.3.2. Time Period and Frequency for Collecting Safety Event Information

- AEs/AESIs/SAEs/Special Situations will be collected from the signing of the ICF until 30 days after the last dose of study treatment.
- Pregnancies will be reported from the first dose of study treatment until 30 days after the last dose of study treatment. However, if a pregnancy is reported by the participant 30 days after the last dose of study treatment, the pregnancy should still be reported to Safety.
- Investigators are not obligated to actively seek AE or SAE information after conclusion of the study participation. However, if the Investigator learns of any SAE, including a death, at any time after a participant has been discharged from the study, and they consider the event to be reasonably related to the study treatment or study participation, the Investigator must promptly notify Safety.
- All AESIs/SAEs/Special Situations will be reported to the Sponsor's safety group (referred to as 'Safety' throughout this document) within the timeframes as described in [Table 10](#).

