5.6.2. Adverse Events

All AEs will be coded using the MedDRA coding dictionary version 27.0 and displayed in tables and data listings using system organ class (SOC) and preferred term (PT).

Analyses of AEs will be performed for those events that are considered treatment-emergent adverse events (TEAEs), defined as those with initial onset or increasing in severity after the first dose of study treatment through 30 days after the last dose of study treatment. The imputation of partial/missing dates is described in Section 4.9.1.

Treatment-related TEAEs are defined as a TEAE that was considered by the Investigator to be related to the study treatment. If “Relationship to Study Treatment” is missing, it will be imputed as related in summary tables.

AE grade refers to the severity of the AE. The Common Terminology Criteria for Adverse Events (CTCAE) version 5.0 displays Grades 1 through 5 with unique clinical descriptions of severity for each AE based on this general guideline:

- Grade 1 Mild; asymptomatic or mild symptoms; clinical or diagnostic observations only; treatment not indicated.
- Grade 2 Moderate; minimal, local or noninvasive intervention indicated; limiting age-appropriate instrumental Activities of Daily Living (ADL).
- Grade 3 Severe or medically significant but not immediately life-threatening; hospitalization or prolongation of hospitalization indicated; disabling; limiting self-care ADL.
- Grade 4 Life-threatening consequences; urgent intervention indicated.
- Grade 5 Death related to AE.

An event is defined as ‘serious’ when it meets at least 1 of the predefined outcomes as described in the definition of an SAE (Protocol Appendix A5-1.3), not when it is rated as severe.

A summary of TEAEs will include the number and percentage of participants who experience at least one of the following. The total number of events will also be reported.

- TEAEs

- TEAEs related to study treatment
- Serious TEAEs
- Serious TEAEs related to study treatment
- Serious TEAEs by maximum severity (Grade)
- TEAEs with CTCAE grade ≥ 3
- TEAEs with CTCAE grade ≥ 3 related to study treatment
- TEAEs by maximum severity (Grade)
- TEAEs leading to early discontinuation from study treatment
- TEAEs leading to early discontinuation from study treatment related to study treatment
- TEAEs leading to dose reduction
- TEAEs leading to dose reduction related to study treatment
- TEAEs leading to dose interruption

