The number and percentage of participants with concomitant medication used for each safety topic of special interest will be presented by ATC Classification, Preferred Term and Grade (1-2 vs. ≥ 3). The following will be also summarized:

- Number and percentage of participants with the safety topic of special interest
- Time to Onset of First Instance of the safety topic of special interest (days)
- Duration of the safety topic of special interest (days) for each event
- Time from onset of first instance of the safety topic of special interest to resolution of last event
- Number of participants with the safety topic of special interest by outcome, grade (1-2 vs. ≥ 3), and dose modification (if any)
- Number and percentage of participants with concomitant medication use for the safety topic of special interest
- Duration of concomitant medication use for the safety topic of special interest (days)

If an adverse event is ongoing, the end date will be imputed as the data cut-off date for the duration calculation. The duration of concomitant medication use is defined as the number days a participant took medications for the safety topic of special interest. If multiple concomitant medications are taken on a given day, that day will be counted once in the sum. If a medication is ongoing, the end date will be imputed as the last visit date + 28 days (if not before the medication start date), or the study treatment end date if unavailable.

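### SAP 4.9.1 sets some partial adverse event onset dates to the first-dose date without checking the recorded end date, so an event that ended during screening can be counted as treatment-emergent

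*SAP*

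**What the plan says.** SAP 4.9.1 opens by stating what the imputation is for: "Adverse events with incomplete onset dates will be handled as follows for the purpose of determining treatment emergence". Two of its branches lead to the first-dose date.

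- Day and month missing, year equal to the year of first dose: "then the day and month of the first dosing date will be assigned to the missing fields".
- Day only missing: "If the month and year are the same as the month of treatment, the onset date will be assigned to the date of treatment".

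The end date enters only where nothing is known about onset; the condition reads "If the start date is completely missing and end date is not before the first dose of study treatment", and an event meeting it is treatment-emergent. The single limit on an imputed date is death: "If the participant has died and the imputed date is later than the date of death, the date of death will be used".

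SAP 5.6.2 gives this definition of treatment-emergent events: "those with initial onset or increasing in severity after the first dose of study treatment through 30 days after the last dose". For partial dates it refers back to 4.9.1, and it adds no end-date condition. Under Protocol 11.3.2, events "will be collected from the signing of the ICF until 30 days after the last dose of study treatment", so pre-dose events are in the database by design.

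**The concern.** Imputing an unknown onset to first dose is a sensible conservative convention when the timing cannot be settled. Here it can be. If the recorded end date precedes first dose, the event neither began nor worsened on treatment, whatever the missing day was. The rule overrides that information and places onset after the event had ended.

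Section 4.9.1 is also inconsistent with itself. With the start date wholly missing, an end before first dose keeps the event out of the treatment-emergent set. If the site supplies the onset month as well, the same event is counted. More information gives a worse classification.

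At stake is the accuracy of the treatment-emergent tables. The error runs in one direction, towards over-counting. SAP 5.6.2 also imputes a missing causality as related, so a misclassified event without a causality entry would appear among the treatment-related events too.

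**Working it through.** The plan states no figure on this point, so the check applies the rules as written to test dates and then bounds the effect.

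**1. Rules applied literally.** Inputs: the branches of SAP 4.9.1 and the event window of SAP 5.6.2. Illustrative assumption: first dose 20 March 2023, last dose 20 September 2023. The last column adds one condition: a known end before first dose means not treatment-emergent.

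| Case | Recorded onset | Recorded end | Imputed onset | Treatment-emergent under SAP | With end-date check |
|---|---|---|---|---|---|
| A | day missing, March 2023 | 10 March | 20 March | yes | no |
| B | day and month missing, 2023 | 25 February | 20 March | yes | no |
| C | day missing, February 2023 | 25 February | 1 February | no | no |
| D | completely missing | 10 March | none | no | no |
| E | day missing, March 2023 | 25 March | 20 March | yes | yes |
| F | day missing, March 2023 | ongoing | 20 March | yes | yes |

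Cases A and D have the same end date and differ only in that A records the onset month; the SAP classifies them differently. The check changes A and B and leaves the other four alone.

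**2. Calendar exposure.** A missing-day onset can meet the rule only if it falls in the calendar month of first dose. For a first dose on day d of the month, the share of the 28 screening days in that month is min(d − 1, 28)/28: 0/28 = 0% on the 1st, 14/28 = 50% on the 15th, 28/28 = 100% from the 29th. With first-dose dates assumed uniform over the calendar, the average is about 52%. About 96% of screening days share the calendar year, which is what matters when day and month are both missing. These are shares of days, not of events; they show that matching the month or year is no rare coincidence, not that partial dates are common.

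**3. Largest effect on a table row.** SAP 5.8 and Section 6 give 53 enrolled. If all were treated, one extra participant adds 1/53 = 1.9 percentage points. SAP 5.6.2 counts each participant once per preferred term or system organ class, so the addition is 0 when she already has a genuine event in that row.

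**4. Onset and duration summaries.** SAP 5.6.3 lists "Duration of the safety topic of special interest (days) for each event" and time to first onset. If, and only if, the imputed date is reused there, case A has a Day 1 onset and a duration of 10 March − 20 March = −10 days by simple difference.

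**5. Comparison within the SAP.** Rule 4 of SAP 4.9.2 uses the stop date of a concomitant therapy when its start is either completely or partially missing. The check that is absent for partial event onsets is thus already used for medications.

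**The case against.** The strongest reply is that the affected set is narrow. An event needs a partial onset, a known part matching first dose, and a recorded end before first dose. Events are collected prospectively over a screening period of normally at most 28 days, with a baseline visit within 48 hours before dosing. An event recent enough to have a usable end date but no onset day should be uncommon. Prior-month onsets and fully missing starts are already handled correctly. The study is single-arm and descriptive, over-counting cannot hide harm, no efficacy result is touched, and all events appear in listings where an end before first dose would be visible. All of this stands and limits the weight of the point. It does not make the stated rule give the right answer.

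One could also note that an onset imputed to the dosing date is not, by calendar day, after first dose, so 5.6.2 would exclude it. That reading would defeat the stated purpose of the imputation and exclude cases E and F as well, so it is not the natural one.

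Three stronger conclusions might be inferred, and the documents do not support them.

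- That 4.9.1 contradicts the definition in 5.6.2. It fills in unknown dates for that definition and lacks an exception; the inconsistency lies within 4.9.1.
- That negative durations will appear. Section 4.9.1 confines the imputation to deciding treatment emergence, and the date imputations in 5.6.3 concern end dates of ongoing events and medications, so this remains conditional.
- That every misclassified participant adds 1.9 points. That is a ceiling per row, and 53 is the number enrolled, not a stated Safety Analysis Set size.

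**Conclusion.** The point holds as a defect in a stated rule. Followed as written, SAP 4.9.1 classifies as treatment-emergent an event recorded as having ended before first dose whenever its partial onset matches the dosing month, or the dosing year if the month is also missing. The bias is towards over-counting. Its size cannot be derived because no rate of partial dates is given; it is probably a few events or none. The bound is 1.9 percentage points per affected participant in a given row, assuming all 53 enrolled were treated and that she has no genuine event there. A Day 1 onset and a negative duration follow only if the imputed date is carried into the SAP 5.6.3 summaries. The correction is worth making because it is nearly free and aligns the partial-date rules with the condition already applied to fully missing start dates, not because the safety conclusions are likely to change.

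**What to change.** Add to SAP 4.9.1, for every partial onset date: an event whose known or partial end date shows that it ended before first dose is not treatment-emergent, and an imputed onset may not be later than the end date. Keep the first-dose imputation in all other cases, including ongoing events, unknown end dates, and partial end dates that leave the order undecided. The cap also covers the prior-year branch, where 31 December can fall after a recorded end, although classification there is unaffected. It would help to state in SAP 5.6.3 whether imputed onsets feed the time-to-onset and duration summaries.

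The cost is a sentence or two in the SAP and about one line of programming. Data collection and study conduct do not change.
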